# 5. GENERAL METHODOLOGY AND CONVENTIONS

To facilitate rapid review of data in real time, Sponsor staff will be unblinded to study intervention allocation. All laboratory testing personnel performing serology assays will remain blinded to study intervention assigned/received throughout the study. Further details can be found in protocol, Section 6.3. The timing for statistical analyses is specified in Section 7.

# 5.1. Hypotheses and Decision Rules

No hypothesis will be performed testing for this study.

# 5.2. General Methods

Time points for local reactions and systemic events refer to data within 7 days after each dose. CIs for all endpoints in the statistical analysis will be presented as 2-sided at the 95% level unless specified otherwise.

# 5.2.1. Analyses for Binary Data

Descriptive statistics for categorical variables (eg, proportions) are the percentage (%), the numerator (n), and the denominator (N) used in the percentage calculation, and the 95% CIs where applicable.

The exact 95% CI for binary endpoints for each group will be computed using the F distribution (Clopper-Pearson). The 95% CI for the between-group difference for binary endpoints will be calculated using the Miettinen and Nurminen method.

The 3-tier approach will be used to summarize AEs. For both Tier 1 (if any are identified during the study) and Tier 2 events, a 95% CI for the between-group difference in proportions will be calculated based on the Miettinen and Nurminen method. In addition, for Tier 1 events (if any), the asymptotic p-values will also be presented for the difference in proportions, based on the same test statistic and under the assumption that the test statistic is asymptotically normally distributed. For Tier 3 events, counts and percentages for each vaccine group will be provided.

# 5.2.2. Analyses for Continuous Data

Unless otherwise stated, descriptive statistics for continuous variables are n, mean, median, standard deviation, minimum, and maximum.

# 5.2.2.1. Geometric Means

For immunogenicity results of SARS-CoV-2 serum neutralizing titers, the GMTs will be computed along with associated 95% CIs. The GMTs will be calculated as the mean of the assay results after making the logarithm transformation and then exponentiating the mean to express results on the original scale. Two-sided 95% CIs will be obtained by taking log transformations of titers, calculating the 95% CI with reference to the Student's t-distribution, and then exponentiating the confidence limits.

# 5.2.2.2. Geometric Mean Fold Rises

GMFRs will be defined as the result after vaccination divided by the result before vaccination. GMFRs are limited to participants with nonmissing values at both time points.

GMFRs will be calculated as the mean of the difference of logarithmically transformed neutralization titers or antibody levels (later result minus earlier result) and exponentiating the mean. The associated 2-sided 95% CIs are obtained by constructing CIs using the Student's t-distribution for the mean difference on the natural log scale and exponentiating the confidence limits.

# 5.2.2.3. Reverse Cumulative Distribution Curves

Empirical RCDCs will plot proportions of participants with values equal to or exceeding a specified assay value versus the indicated assay value, for all observed assay values. Data points will be joined by a step function with data points on the left side of the step.

# 5.3. Methods to Manage Missing Data

For endpoints, the missing data handling rules are described in the corresponding endpoint sections.

For the missing dates, the sponsor data standard rules for imputation will be applied (eg, partial dates for AEs will be imputed according to Pfizer standard algorithms).

# 6. ANALYSES AND SUMMARIES

Most of immugenicity and safety summaries will be provided by age category (20 to 64 years of age and 65 to 85 years of age) in addition to overall population.

# 6.1. Primary Endpoint(s)

# 6.1.1. Primary Safety Endpoints

The safety analyses are based on the safety population. Participants will be summarized by vaccine group according to the study interventions they actually received. Missing e-diary data will not be imputed; missing AE dates will be handled according to the Pfizer safety rules.

# 6.1.1.1. Local Reactions

# 6.1.1.1.1. Main Analysis

- Estimand: The percentage of participants reporting local reactions (redness, swelling, and pain at the injection site) within 7 days after each dose (Section 2.1).
- Analysis set: Safety population (Section 4).
- Analysis time point: Within 7 days after each dose.
- Analysis methodology: Descriptive statistics (Section 5.2.1).
- Intercurrent events and missing data: The participants without any e-diary data throughout the 7 days after vaccination will be excluded from the analysis at that particular vaccination; missing values will not be imputed.

• Reporting results: Descriptive statistics for each and any local reaction after each dose in each vaccine group will be presented by maximum severity across severity levels. Confirmed e-diary errors will be excluded from the analysis. Descriptive summary statistics will include counts and percentages of participants with the indicated endpoint and the associated 2-sided Clopper-Pearson 95% CIs.

# 6.1.1.1.2. Supplementary Analyses

To support the assessment of local reactions, the following endpoints (as defined in Section 3.1.1.1) will be summarized with the same analysis time point and analysis population, analysis methodology, and appropriate reporting results. Confirmed e-diary errors will be excluded from these analyses.

- Duration (days) of each local reaction after each dose.
- Onset day of each local reaction after each dose.

These continuous endpoints will be summarized by displaying n, mean, median, standard deviation, minimum, and maximum for each vaccine group.

## **Figures:**

Bar charts with the proportions of participants for each local reaction throughout 7 days will be plotted for each vaccine group. The bars will be divided into severity categories to highlight the proportions of participants by maximum severity.

# 6.1.1.2. Systemic Events

#### 6.1.1.2.1. Main Analysis

- Estimand: The percentage of participants reporting systemic events (fever, fatigue, headache, chills, vomiting, diarrhea, new or worsened muscle pain, and new or worsened joint pain) within 7 days after each dose (Section 2.1).
- Analysis set: Safety population (Section 4).
- Analysis time point: Within 7 days after each dose.
- Analysis methodology: Descriptive statistics (Section 5.2.1).
- Intercurrent events and missing data: The participants without any e-diary data throughout the 7 days after vaccination will be excluded from the analysis at that particular vaccination; missing values will not be imputed.
- Reporting results: Descriptive statistics for each systemic event after each dose in each vaccine group will be presented by maximum severity across severity levels. Descriptive summary statistics will include counts and percentages of participants with the indicated endpoint and the associated 2-sided Clopper-Pearson 95% CIs.

# 6.1.1.2.2. Supplementary Analyses

The following endpoints for assessment of systemic events will be summarized similarly to the assessment of local reactions:

- Duration of each systemic event after each dose.
- Onset day of each systemic event after each dose.

These continuous endpoints will be summarized by displaying n, mean, median, standard deviation, minimum, and maximum for each vaccine group.

The use of antipyretic medication (see Section 3.1.1.3) will be summarized similarly to systemic events, except that there is no severity level associated with the use of antipyretic medication.

## **Figures:**

Bar charts with the proportions of participants reporting each systemic event throughout 7 days after each dose will be plotted for each vaccine group. The bars will be divided into severity categories to highlight the proportions of participants by severity.

## 6.1.1.3. Adverse Events

## 6.1.1.3.1. Main Analysis

- Estimand: The percentage of participants reporting AEs from Dose 1 to 1 month after Dose 2 (Section 2.1).
- Analysis set: Safety population (Section 4).
- Analysis time point: Dose 1 to 1 month after Dose 2.
- Analysis methodology: Descriptive statistics (Section 5.2.1) and additional 3-tier approach (Section 3.1.1.4).
- Intercurrent events and missing data: Partial AE dates will be imputed using the Pfizer standard algorithm.

• Reporting results: AEs will be categorized according to MedDRA terms. A 3-tier approach will be used to summarize AEs. Under this approach AEs are classified into 1 of 3 tiers (Section 3.1.1.4). For both Tier 1 and Tier 2 events, 2-sided 95% CIs for the difference between the active vaccine and placebo groups in the percentage of participants reporting the events based on the Miettinen and Nurminen method will be provided. In addition, for Tier 1 events, the asymptotic p-values will also be presented for the difference between groups in the percentage of participants reporting the events, based on the same test statistic and under the assumption that the test statistic is asymptotically normally distributed. AE displays will be sorted in descending order of point estimates of risk difference within the SOC. Descriptive summary statistics (counts, percentages, and associated Clopper-Pearson 95% CIs) will be provided for any AEs for each vaccine group.

## 6.1.1.3.2. Supplementary Analyses

Immediate AEs (within the first 30 minutes after each dose) will also be summarized for each vaccine group. All AEs after informed consent and prior to the first vaccination will not be included in the analyses but will be listed. AESIs will also be listed.

#### 6.1.1.4. Serious Adverse Events

#### 6.1.1.4.1. Main Analyses

- Estimand: The percentage of participants reporting SAEs from Dose 1 to 12 months after Dose 2 (Section 2.1).
- Analysis set: Safety population (Section 4).
- Analysis time point: Dose 1 to 12 months after Dose 2.
- Analysis methodology: Descriptive statistics (Section 5.2.1).
- Intercurrent events and missing data: Partial SAE dates will be imputed using the Pfizer standard algorithm.
- Reporting results: SAEs will be categorized according to MedDRA terms. Counts, percentages, and the associated Clopper-Pearson 95% CIs of SAEs from Dose 1 to 12 months after Dose 2 will be provided for each vaccine group.

#### 6.1.1.5. Hematology and Chemistry Parameters (for Clinical Laboratory Subset)

#### 6.1.1.5.1. Main Analyses

- Estimands: The percentage of participants with abnormal hematology and chemistry laboratory values 1 and 7 days after Dose 1; and 7 days after Dose 2 (Section 2.1).
- The percentage of participants with grading shifts in hematology and chemistry laboratory assessments between baseline and 1 and 7 days after Dose 1; and before Dose 2 and 7 days after Dose 2 (Section 2.1).

- Analysis set: Safety population including clinical laboratory subset only (Section 4).
- Analysis time point: 1 and 7 days after Dose 1; and 7 days after Dose 2.
- Analysis methodology: Descriptive statistics including counts and percentage (Section 5.2.1).
- Intercurrent events and missing data: Missing values will not be imputed.
- Reporting results: Descriptive summary statistics will be provided including counts and percentages of participants with the indicated endpoint and the associated Clopper-Pearson 2-sided 95% CIs for each vaccine group by age category (20 to 64 years of age and 65 to 85 years of age).

#### 6.1.2. Immunogenicity Endpoints

The statistical analysis of immunogenicity results will be primarily based on the Evaluable immunogenicity populations as defined in the protocol, Section 9.3.

An additional analysis will be performed based on the all-available populations if there is a large enough difference in sample size between the all-available immunogenicity population and the evaluable immunogenicity population. Participants will be summarized according to the vaccine group to which they were randomized. Missing serology data will not be imputed.

# 6.1.2.1. SARS-CoV-2 Neutralizing Titers

#### 6.1.2.1.1. Main Analyses

- Estimands:
  - GMTs (Section 2.1).
  - GMFR from before vaccination to 1 month after Dose 2 (Section 2.1).
- Analysis set: Evaluable and all-available immunogenicity populations (Section 4).
- Analysis time points: 1 month after Dose 2.
- Analysis methodology: GMs and the associated 2-sided CIs will be derived by calculating means and CIs on the natural log scale based on Student's t-distribution, and then exponentiating the results (Section 5.2.2.1). GMFRs will be limited to participants with nonmissing values prior to the first dose and at the postvaccination time point. The GMFR will be calculated as the mean of the difference of logarithmically transformed assay results (later time point earlier time point) and exponentiated to transform results back to the original scale. Two-sided CIs will be obtained by calculating CIs using the Student's t-distribution for the mean difference of the logarithmically transformed assay results and exponentiating the confidence limits (Section 5.2.2.2).

- Intercurrent events and missing data: Titers below the LLOQ or denoted as BLQ will be set to  $0.5 \times LLOQ$  for analysis. However, this calculation may be adjusted based upon additional data from the assay. Missing data will not be imputed.
- Reporting results: GMTs 1 month after Dose 2 and GMFR from before vaccination to 1 month after Dose 2 and the associated 2-sided 95% CIs.

# 6.1.2.1.2. Additional Exploratory Analyses

Similar analysis for SARS-CoV-2 serum neutralizing titers may be performed by baseline SARS-CoV-2 status (positive or negative). Positive SARS-CoV-2 at baseline is defined by a positive N-binding antibody result or positive NAAT result at baseline.

#### 6.2. Secondary Endpoints

#### 6.2.1. Immunogenicity Endpoints

## 6.2.1.1. SARS-CoV-2 Serum Neutralizing Titers

#### 6.2.1.1.1. Main Analyses

- Estimands:
  - GMTs (Section 2.1).
  - GMFR from before vaccination to each subsequent time point after vaccination (Section 2.1).
- Analysis set: Evaluable and all-available immunogenicity populations (Section 4).
- Analysis time points: Baseline and 21 days after Dose 1; 7 and 14 days and 6, and 12 months after Dose 2.

Analysis methodology, intercurrent events and missing data, and reporting results should be referred to Section 6.1.2.1.1.

#### 6.2.1.1.2. Additional Exploratory Analyses

Similar analysis for SARS-CoV-2 serum neutralizing titers may be performed by baseline SARS-CoV-2 status (positive or negative). Positive SARS-CoV-2 at baseline is defined positive N-binding antibody result or positive NAAT result at baseline. However, if the number of participants with baseline SARS-CoV-2 positive status is less than 10, the summary will not be performed.

#### 6.2.1.1.3. Subgroup Analyses for Participants With/Without Confirmed COVID-19 Before Dose 2

Primary/secondary endpoints for SARS-CoV-2 serum neutralizing titer will be performed by subgroup of participants with/without confirmed COVID-19 before Dose 2) as described in Section 3.2. However, if the number of participants with confirmed COVID-19 before Dose 2 is less than 10, only listings will be displayed.

The definition to include participants for the subgroup analysis is described in Section 3.2.

# 6.3. Exploratory Endpoints

## 6.3.1. Immunogenicity Endpoints

#### 6.3.1.1. SARS-CoV-2 Serum Neutralizing Titers

# **6.3.1.1.1.** Subgroup Analyses for Participants With/Without Confirmed COVID-19 During the Study

Primary/secondary endpoints for SARS-CoV-2 serum neutralizing titer will be performed by subgroup of participants with/without confirmed COVID-19 during the study as described in Section 3.1.1. However, if the number of participants with confirmed COVID-19 during the study is less than 10, only listings will be displayed.

The definition to include participants for the subgroup analysis is described in Section 3.1.1.

## 6.3.1.2. SARS-CoV-2 N-Binding Antibody

- Estimands:
  - Percentage of participants with seroconversion by N-binding antibody.
- Analysis set: Participants with seroconversion with/without confirmed COVID-19 during the study in evaluable and all-available immunogenicity populations (Section 4). However, if the number of participants with confirmed COVID-19 during the study is less than 10, the summary will be performed for the participants without confirmed COVID-19 during the study in evaluable and all-available immunogenicity populations (Section 4).
- Analysis time points: Baseline and 21 days after Dose 1; 7 and 14 days and 1, 6, and 12 months after Dose 2.
- Analysis methodology: Descriptive statistics (Section 5.2.1).
- Intercurrent events and missing data: Titers/concentrations below the LLOQ or denoted as BLQ will be set to 0.5 × LLOQ for analysis. However, this calculation may be adjusted based upon additional data from the assay. Missing data will not be imputed.
- Reporting results: Percentages of participants with seroconversion will be calculated with the associated 2-sided 95% CIs (Clopper-Pearson method) at each time point after vaccination.

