From protocol amendment 3, this study is transitioned from a clinical trial to a postmarketing study according to the Japanese regulation, because BNT162b2 was approved by the MHLW on 14 February 2021.

All participants will be informed of their original study intervention allocation (BNT162b2 or placebo) by the site staff. All participants who originally received placebo will be offered the opportunity to receive BNT162b2 at their earliest convenience as part of the study (administration of BNT162b2 before the 6-month follow-up visit [Visit 8 for the clinical laboratory subset or Visit 6 for the standard participants] is allowed). If they want to receive BNT162b2, they will move to the SoA in Section 1.3.3 for their remaining visits. Participants who originally received BNT162b2 and placebo recipients who decline BNT162b2 vaccination will continue in the study as originally planned.

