# 8.11.1.11. Visit 9 – 12-Month Follow-up Visit (350 to 378 Days After Visit 4): Only for Those Participants Who Originally Received BNT162b2 or Placebo Recipients Who Decline BNT162b2

- Record SAEs as described in Section 8.3.
- Collect a blood sample (approximately 25 mL) for immunogenicity testing.
- Confirm details of any of the prohibited medications specified in Section 6.5.1 received by the participant if required for his or her clinical care.
- Collect the participant's e-diary or assist the participant to remove the study application from his or her own personal device.
- Complete the source documents.
- The investigator or an authorized designee completes the CRFs.

• Record any AEs that occur within the 48 hours after the blood draw as described in Section 8.3.

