	For SARS-CoV-2 serum neutralizing titers, the GMFRs and 2-sided 95% CIs will be provided for each group at each of the following time points:		
	• To 21 days after Dose 1, and 7 and 14 days and 6 and 12 months after Dose 2, from the prevaccination time point		
	GMFRs will be calculated using the same methodology as described for the primary endpoints.		
	GMTs and GMFRs of SARS-CoV-2 serum neutralizing titers for participants with/without confirmed COVID-19 before Dose 2		
	GMTs, GMFRs, and their 2-sided 95% CIs will be provided for each group at each of the time points for participants with and without confirmed COVID-19 before Dose 2.		
	GMTs and GMFRs will be calculated using the same methodology as described for the primary endpoints.		
Exploratory	GMTs and GMFRs of SARS-CoV-2 serum neutralizing titers for		
immunogenicity	participants with/without confirmed COVID-19 during the study		
	GMTs, GMFRs, and their 2-sided 95% CIs will be provided for each group at each of the time points for participants with and without confirmed COVID-19 during the study.		
	GMTs and GMFRs will be calculated using the same methodology as described for the primary endpoints.		

Endpoint	Statistical Analysis Methods	
	Percentage of participants with the immune response (non-S) to SARS-CoV-2 for N-binding antibody at the time points for participants with/without confirmed COVID-19 during the study when data are available	
	The Clopper-Pearson method will be used to calculate the CIs.	
	RCDCs for immunogenicity results	
	Empirical RCDCs will be provided for SARS-CoV-2 serum neutralizing titers after Dose 2.	

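### When at least 10 participants have confirmed COVID-19, SAP 6.3.1.2 computes the percentage with N-binding seroconversion among participants who have seroconverted, so the outcome defines its own denominator

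*SAP*

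**What the plan says.** SAP 6.3.1.2 covers the N-binding antibody summary, which serves the exploratory objective on the non-S response in participants with and without confirmed COVID-19.

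- **Estimand:** "Percentage of participants with seroconversion by N-binding antibody".
- **Analysis set, main branch:** "Participants with seroconversion with/without confirmed COVID-19 during the study in evaluable and all-available immunogenicity populations".
- **Switch to the fallback:** it applies "if the number of participants with confirmed COVID-19 during the study is less than 10". The main branch therefore needs 10 or more.
- **Analysis set, fallback:** "the summary will be performed for the participants without confirmed COVID-19 during the study in evaluable and all-available immunogenicity populations".
- **Reporting:** "Percentages of participants with seroconversion will be calculated with the associated 2-sided 95% CIs (Clopper-Pearson method) at each time point after vaccination".

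SAP 3.3.1 defines seroconversion as a positive N-binding result after vaccination in a participant who was negative at baseline. It places the N-binding assay among the exploratory endpoints to be described in evaluable participants with or without confirmed COVID-19. Protocol 9.4.1 describes the same analysis as "Percentage of participants with the immune response (non-S) to SARS-CoV-2 for N-binding antibody at the time points", for participants with or without confirmed COVID-19. The SAP version history records that version 2 updated the analysis set of Section 6.3.1.2, so the line is current text.

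**The concern.** Seroconversion is a post-vaccination outcome, yet the main branch uses it to decide who is counted. A percentage of responders among responders cannot estimate how often participants respond. The objective is to see how common the non-S response is in those with and without confirmed COVID-19, and the main branch as worded cannot show that in either group.

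The two branches of the bullet also disagree. Participants without confirmed COVID-19 appear in both, with a full denominator if 9 cases occur and a responder-only denominator if 10 occur. The same table row would change meaning with one more case.

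**Working it through.** The plan states no figure for N-binding seroconversion, so there is nothing to reproduce on the point itself. The check compares the passages, then works through what the literal line would print.

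**1. Which lines restrict to seroconverters?**

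| Place | Participants described | Limited to seroconverters? |
|---|---|---|
| SAP 6.3.1.2, main branch | with/without confirmed COVID-19 | Yes |
| SAP 6.3.1.2, fallback | without confirmed COVID-19 | No |
| SAP 3.3.1 | evaluable, with/without confirmed COVID-19 | No |
| Protocol 9.4.1 | with/without confirmed COVID-19 | No |
| SAP Section 4 | evaluable and all-available sets | No; no seroconverter set is defined |
| SAP 5.2.1 | n, N and % to be shown | Does not say which N applies |

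Only the main branch carries the restriction. The other places show the intended set.

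**2. What the literal line gives.** There are two readings.

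- *Applied at each time point.* Numerator and denominator are the same x participants, so the result is x/x = 100% for any x of at least 1, and 0/0 where x = 0. The Clopper-Pearson lower limit is then 0.025^(1/x), which depends only on x: 2.5% for x = 1, 47.8% for x = 5, 69.2% for x = 10.
- *Applied once per participant (ever seroconverted).* This fits the way SAP Section 4 defines populations. If S participants ever seroconvert and k of them are positive by a visit, the result is k/S, which describes timing among responders.

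**3. Illustration. All counts of cases and seroconverters are assumed.** Protocol 9.2 expects 160 × 0.9 = 144 evaluable participants (120 × 0.9 = 108 vaccine, 40 × 0.9 = 36 placebo). Assume 10 have confirmed COVID-19, which leaves 144 − 10 = 134 without. Assume 8 and 3 eventually seroconvert, of whom 5 and 1 have done so by an earlier visit. Arms are pooled, and everyone is taken as baseline-negative with a valid result. Cells show % (95% Clopper-Pearson CI).

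| | With confirmed COVID-19 | Without |
|---|---|---|
| Earlier visit, ever seroconverted | 5/8 = 62.5 (24.5–91.5) | 1/3 = 33.3 (0.8–90.6) |
| Earlier visit, per time point | 5/5 = 100 (47.8–100) | 1/1 = 100 (2.5–100) |
| Earlier visit, no restriction | 5/10 = 50.0 (18.7–81.3) | 1/134 = 0.7 (0.0–4.1) |
| Last visit, either literal reading | 8/8 = 100 (63.1–100) | 3/3 = 100 (29.2–100) |
| Last visit, no restriction | 8/10 = 80.0 (44.4–97.5) | 3/134 = 2.2 (0.5–6.4) |

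At 6 and 12 months the 134 may be smaller. For placebo recipients, "If they want to receive BNT162b2, they will move to the SoA in Section 1.3.3 for their remaining visits", and the 12-month visit is headed "Only for Those Participants Who Originally Received BNT162b2 or Placebo Recipients Who Decline BNT162b2". If all 36 evaluable placebo recipients crossed over and all 10 cases were in the vaccine arm, the group without confirmed COVID-19 would be 108 − 10 = 98, and the unrestricted figures would be 1/98 = 1.0% (0.0–5.6) and 3/98 = 3.1% (0.6–8.7). The loss at 6 months may be less than complete, because Visit 101 can coincide with that visit and includes an immunogenicity sample unless one was taken in the previous 7 days.

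**4. Would the main branch be used?** The documents give no case rate. The bullet names both immunogenicity populations, so take N = 144 (evaluable) and N = 160 (ceiling for all-available). The binomial probability of 10 or more cases is:

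| Assumed rate | N = 144 | N = 160 |
|---|---|---|
| 3% | 0.012 | 0.023 |
| 5% | 0.19 | 0.28 |
| 7% | 0.56 | 0.69 |
| 10% | 0.92 | 0.96 |

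The branch could be nearly certain or nearly excluded, depending on a rate that the plan does not state.

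**The case against.** The strongest reply is that the intention is plain. SAP 3.3.1 states the population for this endpoint without restriction, Protocol 9.4.1 agrees, the fallback agrees, and the estimand and reporting bullets treat seroconversion as the outcome. A programmer who produced a table at or near 100% would probably query it. All of this stands, and it is why the point is one of wording. It does not remove the conflict: the analysis-set bullet is the instruction that gets programmed, and nothing says that SAP 3.3.1 overrides it.

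Three stronger readings are tempting, and the documents do not support them.

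- *The plan as a whole adopts a responder-only denominator.* It does not. One line does, against several others.
- *Every post-vaccination percentage would be 100%.* That follows only if the set is formed at each visit, and even then a visit without seroconverters gives 0/0. If the set is formed once, percentages below 100% are possible.
- *The rate without confirmed COVID-19 would be inflated by a known multiple.* Any such multiple is the full denominator divided by the assumed number of eventual seroconverters. The count at the visit cancels, so the multiple only restates the assumption.

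**Conclusion.** The point holds as an error in an operative SAP line: in the main branch, the analysis set is conditioned on the outcome being estimated. Either literal reading fails to give the stated estimand, and this conclusion needs no assumption about counts.

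Its importance is minor. The summary is exploratory and descriptive, it applies only with 10 or more confirmed cases, and no primary or secondary result depends on it. The illustrative percentages and branch probabilities rest on assumed counts and rates. They show the kind of distortion, not its size.

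**What to change.** In the analysis-set bullet of SAP 6.3.1.2, delete the words *with seroconversion* and state the denominator. The set would then be participants with or without confirmed COVID-19 during the study, in the evaluable (and all-available) immunogenicity populations, who have a negative N-binding result at baseline and a valid N-binding result at the time point. Seroconversion is the numerator only. The baseline-negative condition follows from the definition in SAP 3.3.1, since nobody else can seroconvert. Use the same denominator in the fallback branch, so that the row for participants without confirmed COVID-19 means the same thing whichever branch applies.

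The cost is a short edit to one SAP bullet. It needs no new data and no protocol amendment, and it brings the SAP into line with Protocol 9.4.1.
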